### **Adverse Event and Serious Adverse Event Collection and Reporting**

Adverse events will be tracked on an ongoing basis for the full sample using an adapted version of the NIA Adverse Event Form (<https://www.nia.nih.gov/research/dgcr/clinical-research-study-investigators-toolbox/adverse-events>) and serious adverse events will be tracked using the NIH Serious Adverse Event Form

(<https://www.nia.nih.gov/research/dgcr/clinical-research-study-investigators-toolbox/adverse-events>). Adverse events will be reviewed during semi-annual meetings of the Data Safety Monitoring Committee (see 3.0 below for details). The PI will be informed of serious adverse events as soon as they occur and will notify the Safety Officer (Chair of the Committee) within 24 hours of notification. In addition, adverse events and serious adverse events will be reported to the UIC IRB and NIA consistent with their established protocols and will use the NIA AE/SAE Flow Process to guide this process and timeline (<https://www.nia.nih.gov/research/dgcr/clinical-research-study-investigators-toolbox/adverse-events>).

AEs will be defined as any health-related event that occurs within the intervention or assessment measure sessions. Expected AEs may include strained or sore muscles and fatigue. AE severity will be classified as:

- Mild - if the symptoms are tolerated and do not interfere with the participant's daily life.
- Moderate – if the symptoms cause some concern or some disruption to the participant's daily life, but can be alleviated through rest or relatively simple non-medical intervention.
- Severe – if the symptoms cause a major disruption in their daily life and require medical intervention or drug therapy.

All AEs will be documented using the Adverse Event Form by the PI. The PI will assess the relatedness of the AE to the study intervention and the expectedness of the AE. The PI will follow the Adverse Event flow chart to determine routing and reporting of the AE. All AEs will be reported to the DSMC and IRB in accordance with reporting guidelines.

SAEs are not expected to occur within this intervention. However, potential SAEs could be a serious injury related to the intervention, a cardiac event resulting from physical activity, and death. All SAEs will be documented in the Serious Adverse Event form and reported to the NIA program officer and Safety Officer within 48 hours. All participant deaths will be reported to the NIA program officer and Safety Officer within 24 hours. All SAEs will be reported to the DSMC and IRB in accordance with reporting guidelines.

In addition to holding semi-annual DSMC meetings, all AE and SAE data will be reported quarterly by the pilot PI to the NIA project officer and Safety Officer.

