### **6.0 Study Design and Procedures**

This research will be performed via telephone/video conference to maximize social distancing and participant safety. The intervention will be performed by the participants at home.

This is a pilot randomized, controlled trial of a 6-week intervention for feasibility. Outcome measures will be obtained at baseline and at 6-weeks. Behavior choices and preference data will be continuously captured during the intervention. We will randomize 80 older Latinos from the Chicago Latino community to either an ecological momentary intervention using fitbits (n=40) or to physical activity guidelines (n=40).

Study interaction 1-baseline test (Approximately 2 hours). Participants will be screened for inclusion/exclusion criteria. If criteria for inclusion in the study are met participants will undergo informed consent process. Following informed e-consent conducted via zoom video/telephone participants will be asked about their demographics (demographic

form), and contact information (Face sheet), and then they will be asked about their medical history. Following the medical history we will fill out the Charlson co-morbidity questionnaire, and conduct the following cognitive function measures as approved by the NIH for use via video call: a. Picture vocabulary test, b. Picture sequence test, c. List sorting test, d. Oral reading recognition test, e. Auditory verbal learning test, and the Trail Making test A and B. Following the cognitive function testing, we will conduct a phone/video interview. The interview will be recorded, analyzed and used to develop the intervention.

Following the interview we will conclude the phone call and send the participants an activity monitor to be worn on the waist for 8 days to measure sedentary time: The participants will mail the monitor back to us after 8 days. Once we have received the physical activity monitor we will randomize the participant to intervention or control.

**Optional in-person visit (approximately 1 hour) If the participant is willing and able to undergo an MRI scan. No contrast will be used.**

- The MRI Visit will take place about one-week after the initial phone call. Participants will come to the Magnetic Resonance Imaging Center, 3T research center [name] and return the actigraph to us. We will ask participants to do the following:

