**Practitioner). Ultimately, however, it is up to the participant to follow-up with a doctor for a clinical evaluation**

**Following the MRI, we will assess cognitive and basic motor function using the NIH toolbox the NIH Toolbox measures for Cognitive function will completed using the standard NIH Ipad (see administration manual):**

- **C.2.2 NIH Toolbox Flanker Inhibitory Control and Attention Test page 67**
- **C.2.4 NIH Toolbox Dimensional Change Card Sort Test (DCCS) page 98**
- **C.2.5 NIH Toolbox Pattern Comparison Processing Speed Test page 124**
- **C.2.7 NIH Toolbox Oral Reading Recognition Test page 151**
- **C.2.8 Oral Symbol Digit Test page 154**

**Following the NIH Toolbox measures for Cognitive function, the NIH toolbox motor measures will completed using the standard NIH Ipad (see administration manual):**

- **Pegboard dexterity test (172)**
- **Balance measures with the addition of iPod app for assessment of sway (179).**
- **Two-minute walk (198)**
- **Grip strength (using handheld dynamometer, 176)**
- **4 meter walk (195)**

**Study interaction 2 (Approximately 1 hour):** Participants will be notified via telephone which group that were randomized to.

Participants randomized to the intervention group will be sent a fitbit that has been set up to deliver the intervention as described below. We will schedule a telephone call or zoom video call (whichever the participant prefers) to set up the HIPPA compliant EMA system and to provide education about the fitbit and the intervention to disrupt sedentary time.

**Intervention (home-setting):** We will deliver content in real-time, and in the real-world environment using a wearable sensor, an activity tracker and the Illumivu mEMA smart phone app, which will enable real-time delivery of behavior options and real-time feedback on the effectiveness of behavior choices. Although the intervention will be guided by the interview findings, in general, participants will wear a Fitbit that has been programmed to deliver a notification (a buzz) when activity has ceased for more than 10 minutes. They will receive suggestions on their smartphone app on how to replace sitting time with PA such as standing up 5 times or taking 20 steps, or even performing a short (20 seconds) preferred dance routine. We will capture Fitbit data in a real-time platform (ICardia). Participants will receive reminders from their smartphones to enter

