real-time feedback on activity options selected and how successful they were in adopting the option. These data will allow us to track underlying preferences for behaviors and tailor the program accordingly. Participants will receive a message immediately with positive choices for behavioral action. Resulting actions and delivery of the intervention will be automatically captured and downloaded in real time. We will teach them how to use these devices once they are assigned to the intervention group. The sensor and activity tracker will record their everyday physical activity level. When participant stays sedentary too long during a day, the smartphone app will send a real-time reminder with some physical activity options for participant to choose designed based on their preferences and focus group discussions (e.g., standing up 5 times, taking 20 steps, or performing a short dance routine). Resulting actions and delivery of the intervention will be automatically captured and downloaded into the devices in real time.

Participants randomized to the control group will be sent general guidelines for disruption of sedentary time.

Study interaction 3-Follow-up (Approximately 1 hour): At the completion of the 6-week intervention period all participants will be sent an activity monitor to be worn on the waist for 8 days to measure sedentary time: The participants will mail the monitor back to us after 8 days. Once we have received the physical activity monitor we will schedule a phone interview with the participants to understand where they had difficulty and what did or did not work for them. We will then repeat the cognitive function tests and the optional MRI scan.

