### **1.3 Protection Against Study Risks.**

Informed Consent Process. Potential participants will be provided with a copy of the consent form approved by the UIC IRB to follow during the verbal description and also to read on their own. A member of the research team will fully describe the study to the

potential participant(s) verbally, covering all of the content in the consent form, including potential risks and benefits. Potential participants will be given time to read the consent form and invited to ask any questions they may have about the study. Questions will be answered and any identified misunderstandings about the study will be clarified. Individuals interested in participating at this point will be asked to sign the e-consent and will be provided with one copy for their use. The standard consent form template used by the UIC IRB includes all of the basic sections identified in the NIA Informed Consent Checklist (<https://www.nia.nih.gov/research/dgcr/clinical-research-study-investigators-toolbox/informed-consent>).

**Protections Against Study Risk.** We believe that the potential risks to participants in this study are minimal and are risks that anyone disrupting sedentary time is likely to experience. There may be a small risk of muscle soreness associated with increased physical activity. Participants will be encouraged to (a) consult their health care provider before initiating any new physical activity; and (b) perform physical activities at a pace that is comfortable for them and in a way that is consistent with any recommendations from their medical provider.

Special care will be taken to ensure confidentiality of all data as described above. All project staff will be required to be current in training in Human Research Subjects protection sponsored by the University of Illinois at Chicago. The staff will also receive additional training on confidentiality by the principal investigator.

We do not anticipate any serious adverse events or distress as a result of participating in the proposed research. Any concerns will be immediately reported the principal investigator.

**Interim Analysis will not be performed.** The pilot intervention will last 6 weeks. The assessments will occur on two occasions (i.e., baseline; immediately post-intervention), so there will not be an opportunity to do an interim analysis during this short term pilot study.

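### The adverse event definition is tied to sessions; this does not fit an unsupervised home programme with a guidelines-only control and conflicts with the plan's own full-sample tracking

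*Combined protocol and SAP*

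**What the plan says.** The definition is in Section 11.0, under Adverse Event and Serious Adverse Event Collection and Reporting: "AEs will be defined as any health-related event that occurs within the intervention or assessment measure sessions". The same subsection opens with a wider statement, "Adverse events will be tracked on an ongoing basis for the full sample", and names the events it has in mind: "Expected AEs may include strained or sore muscles and fatigue". It grades severity by how far symptoms disturb daily life. The subsection headed 1.3 Protection Against Study Risks says where soreness would come from: "There may be a small risk of muscle soreness associated with increased physical activity".

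Section 6.0 describes the setting: "The intervention will be performed by the participants at home". The Fitbit is "programmed to deliver a notification (a buzz) when activity has ceased for more than 10 minutes", and the app then suggests short activities. For the comparator, "Participants randomized to the control group will be sent general guidelines for disruption of sedentary time". The follow-up paragraph of Section 6.0 refers to the six-week intervention period for all participants, after which everyone wears an activity monitor for 8 days and then has the follow-up interview and tests.

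The opening of Section 11.0 has participants asked, at the phone call and at 6 weeks, about emergency visits, hospitalisations and cardiac-type symptoms. It limits these questions neither by arm nor by session.

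**The concern.** A session-based definition suits a supervised exercise class. Here the activity that could cause soreness, strain or fatigue takes place at home, when the device prompts it. The definition is the rule for what counts as an AE, so staff who follow it to the letter could leave such complaints off the form, or record them in one arm only.

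At stake is the non-serious AE record that goes to the Safety Officer, the DSM Committee, NIA and the IRB. Under SO Responsibilities, the committee weighs participant risk against benefit and may advise on continuation from observed adverse effects. Under Protection of Confidentiality, its data are presented blinded, without saying whether to arm or only to identity. If to arm, a literal application gives the committee a pooled total that is too low. If only to identity, a listing by arm could compare unequal amounts of time. Section 7.0 states that the activities carry no known risks, so a nearly empty record produced by the definition could be mistaken for confirmation.

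**Working it through.** The plan gives no AE rate, and no calculation of its own depends on this definition, so there is no stated figure to reproduce. The check compares the texts and then works out what each reading makes countable.

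**Step 1. Possible readings.**
- *Sessions only.* Sessions governs both intervention and assessment. After randomisation this leaves the EMI set-up call and the follow-up contact. Home events are not AEs in either arm.
- *While the EMI runs.* Within the intervention means during the programme. EMI participants are countable for the six weeks; controls, who have no programme, only at assessments.
- *Symmetric.* The intervention period is taken as six weeks for everyone, and tracking as continuous. Both arms are countable throughout. The surrounding text favours this, but it needs words that the definition lacks.

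**Step 2. Inputs (Section 6.0, approximate durations).** Intervention 42 × 24 = 1,008 h. Follow-up monitor wear 8 × 24 = 192 h. Follow-up contact f = 1 h, or 2 h with the optional visit. Set-up call 1 h, EMI only, at the start of the six weeks. Total after randomisation T = 1,008 + 192 + f = 1,201 to 1,202 h. Arms of 40 each are weighted equally, with full retention assumed.

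**Step 3. Share of T in which a non-serious event would count.**

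| Reading | 8-day wear counted as assessment? | EMI | Control | Pooled |
|---|---|---|---|---|
| Sessions only | No | (1 + f)/T = 0.17% to 0.25% | f/T = 0.08% to 0.17% | 3/2,402 to 5/2,404 = 0.12% to 0.21% |
| Sessions only | Yes | (193 + f)/T = 16.2% | (192 + f)/T = 16.1% | 387/2,402 to 389/2,404 = 16.1% to 16.2% |
| While the EMI runs | No | (1,008 + f)/T = 84.0% | f/T = 0.08% to 0.17% | 1,010/2,402 = 42% |
| While the EMI runs | Yes | T/T = 100% | (192 + f)/T = 16.1% | 1,394/2,402 = 58% |
| Symmetric | Yes | 100% | 100% | 100% |

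In the fourth row the ratio between arms is 1,201/193 = 6.2.

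**Step 4. Sensitivity.** Mailing and scheduling time is not given. Adding 14 uncounted days (an assumption; 336 h, T = 1,537 h) gives pooled shares of 1,010/3,074 = 33% and 1,394/3,074 = 45% while the EMI runs, and 3/3,074 = 0.1% and 387/3,074 = 13% for sessions only. The 6.2 ratio does not move.

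**Step 5. What other routes catch.** Besides the questions to participants, Section 11.0 sends unanticipated adverse events or problems to the IRB within 7 days. The subsection headed 1.3 sends any concern to the principal investigator at once. Section 13.3 covers serious unanticipated related events within 48 hours and other unanticipated events at continuing review. None is limited to sessions. None is aimed at expected, mild complaints, and Section 11.0 names no question on soreness, strain or fatigue.

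**The case against.** The strongest reply is that the context already settles the meaning. Reading the definition as covering the EMI arm only contradicts tracking of the full sample. Reading it as sessions only contradicts ongoing tracking and leaves grading by effect on daily life with little to grade. What is recorded also depends on the adapted NIA form, the AE flow process and the attached checklist, none of which is shown; the checklist may already ask about soreness or fatigue. The follow-up interview about difficulties may bring out some complaints as well. No between-arm AE test is planned, and the listed content of the Safety Officer report does not require AEs by arm.

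Most of this stands. It makes the symmetric reading the probable intent and confines the gap to mild, expected, non-serious events. It does not cure the text: a statement on how AEs are tracked does not define what an AE is, and the two sentences pull apart within one subsection.

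The objection is also right about the percentages. They are clock hours, sleep included, under assumed literal readings. They would be expected shares of events only if events were spread evenly over time, which fits poorly with events linked to activity.

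**Conclusion.** The definition does not fit the design and conflicts with the plan's own statement on tracking. It should be corrected as a minor to moderate matter of safety reporting. The consequence is limited to the completeness and between-arm comparability of soreness, strain, fatigue and similar mild events. No feasibility or cognitive result depends on it.

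A reader might infer that the trial will miss nearly all non-serious home events, or will count the arms at 6.2 to 1. The documents do not support that. It requires staff to apply a literal reading against the surrounding text, and it requires the unseen form and checklist to add nothing. The pooled range, from about 0.1% to 58% under the literal readings against 100% under the symmetric one, shows how much hangs on the wording. It does not measure lost events.

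The conclusion rests on there being no intervention sessions after the set-up call, as Section 6.0 describes, and on the definition being the operative rule for the AE form.

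**What to change.** 1. Define an AE in both arms as any untoward health event from the first study procedure after consent through the last follow-up assessment, whatever the setting. Make clear that this includes baseline testing, both monitor wears and the optional visit. For a participant who withdraws, end the window at the last contact.
2. Record the date of each event. Section 6.0 places allocation after the baseline wear ("Once we have received the physical activity monitor we will randomize the participant to intervention or control"), so any descriptive AE summary by arm should use only events after randomisation.
3. Unless the Section 11.0 checklist already does so, ask about muscle soreness or strain, fatigue and injury in the same words in both arms at the existing six-week contact.
4. If data were already collected under the current definition, compare across arms only the items asked of everyone under Section 11.0, and list other AEs without a comparison.

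The cost is an IRB amendment to the definition and perhaps the checklist, a few questions on a call that already takes place, and more minor background events to document, judge for relatedness and report quarterly.

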### **1.3 Protection Against Study Risks.**

Informed Consent Process. Potential participants will be provided with a copy of the consent form approved by the UIC IRB to follow during the verbal description and also to read on their own. A member of the research team will fully describe the study to the

potential participant(s) verbally, covering all of the content in the consent form, including potential risks and benefits. Potential participants will be given time to read the consent form and invited to ask any questions they may have about the study. Questions will be answered and any identified misunderstandings about the study will be clarified. Individuals interested in participating at this point will be asked to sign the e-consent and will be provided with one copy for their use. The standard consent form template used by the UIC IRB includes all of the basic sections identified in the NIA Informed Consent Checklist (<https://www.nia.nih.gov/research/dgcr/clinical-research-study-investigators-toolbox/informed-consent>).

**Protections Against Study Risk.** We believe that the potential risks to participants in this study are minimal and are risks that anyone disrupting sedentary time is likely to experience. There may be a small risk of muscle soreness associated with increased physical activity. Participants will be encouraged to (a) consult their health care provider before initiating any new physical activity; and (b) perform physical activities at a pace that is comfortable for them and in a way that is consistent with any recommendations from their medical provider.

Special care will be taken to ensure confidentiality of all data as described above. All project staff will be required to be current in training in Human Research Subjects protection sponsored by the University of Illinois at Chicago. The staff will also receive additional training on confidentiality by the principal investigator.

We do not anticipate any serious adverse events or distress as a result of participating in the proposed research. Any concerns will be immediately reported the principal investigator.

**Interim Analysis will not be performed.** The pilot intervention will last 6 weeks. The assessments will occur on two occasions (i.e., baseline; immediately post-intervention), so there will not be an opportunity to do an interim analysis during this short term pilot study.

### **Data and Safety monitoring.**

The pilot Principal Investigator (PI) will be responsible for ensuring participants' safety on a daily basis. The pilot will be monitored by a local Data Safety Monitoring Committee and Safety Officer that will not require approval by the NIA. The Safety Officer in conjunction with a Data Safety Monitoring Roybal Center Committee will act in an advisory capacity to the NIA Director to monitor participant safety, evaluate the progress of the study, to review procedures for monitoring the confidentiality of the data, the quality of data collection matter, management, and analyses.

### **Frequency of Data and Safety Monitoring/ Safety Officer (SO) Reports.**

The pilot PI will meet semi-annually with the DSM Committee, either in-person or by teleconference call, to review study progress, data quality, and participants' safety. Written summary reports will be submitted twice a year and will include a detailed analysis of study progress, data and safety issues. [name] will

serve as chair of the committee, and as SO for any adverse event reports. Other members will include [name] (Roybal PI, SPH); [name] (SPH); and [name] (Nursing).

The PI will be informed of serious adverse events as soon as they occur and will notify the SO within 48 hours. In addition, serious adverse events will be reported to the UIC IRB and NIA consistent with their established protocols.

In addition to semi-annual DSMC meetings, all AEs and SAEs will be reported quarterly to the Safety Officer and NIA project officer.

